## **6.3.2** Safety Assessments

The objective of the safety assessments was to evaluate the safety and tolerability of tarloxotinib in this population, including to determine whether there is an association between plasma exposure to tarloxotinib and effects on cardiac repolarization. Safety was assessed by repeated clinical evaluations including adverse events (AEs), suspected adverse reactions, unexpected events, serious AEs (SAEs), serious unexpected suspected adverse reactions, vital signs, physical examination, ECGs, clinical laboratory tests (serum chemistry, hematology, and urinalysis).

## 6.3.2.1 Adverse Events

Investigators collected information related to AEs throughout this clinical trial. All AEs occurring in all subjects were collected following exposure to study treatment (treatment emergent) until approximately 30 days after the last study treatment.

## 6.3.2.2 Vital Signs

Vital signs were obtained at each visit and prior to and following the start of each tarloxotinib infusion. Vital signs measured include: blood pressure (systolic and diastolic; mmHg); heart rate (beats per minute); body temperature (°C); respiration rate (breaths per minute); and weight (kg).

## **6.3.2.3** Physical Examinations

Complete physical examinations, including a review of all body systems, was performed at the Screening, Day 1 of all cycles, and the end of treatment (EOT) visits as shown in Table 2. Clinically significant findings observed during physical examination were reported as medical history (pre-treatment) or AEs (post-treatment).

## 6.3.2.4 Electrocardiograms

All 12-lead ECG tracings were performed once at the following visits: Screening, EOT, and Safety Follow-up. During Cycle 1, ECGs were performed at five time points (preinfusion, end of infusion [EOI], 1 hour after EOI, 2 hours after EOI, 3 hours after EOI, 4 hours after EOI), and hourly thereafter as needed. After Cycle 1, all treatment visits have ECGs performed at a minimum of three time points (preinfusion, 2 hours after EOI, 4 hours after EOI) and hourly thereafter as needed, as shown in Table 2.

#### **6.3.3** Pharmacokinetic Measurements

Blood samples for tarloxotinib and tarloxotinib-E plasma concentrations were collected prior to and following tarloxotinib infusion on Cycle 1 Day 1 and Cycle 2 Day 1. Serum potassium samples were also collected after the infusion. All blood samples may be collected within the 5 or 10 minutes (see Table 2) prior to or following the protocol-specified time point.

Plasma samples were collected for evaluation of the pharmacokinetics of tarloxotinib and tarloxotinib-E in tumor tissue. Plasma sample were collected at approximately at pre-infusion, EOI, 3 hours after EOI, and 7 hours after EOT (Cycle 1 Day 1 only) for measurement of tarloxotinib and tarloxotinib-E concentrations at each Cycle 1 Day 1 and Cycle 2 Day 1 visits as indicated in Table 2. An optional tumor biopsy may have been conducted at Cycle 1 Day 15.

#### **6.3.4** Tumor Tissue

All subjects had tumor tissue collected at baseline. Tumor samples obtained during screening may have also been used to determine levels of the reductase, six transmembrane epithelial antigen of the prostate, family member 4 (STEAP4). In addition to the above-mentioned tumor sample, an optional tumor tissue sample for measurement of the active metabolite (tarloxotinib-E) and tarloxotinib may have been collected from consenting subjects on Cycle 1 Day 15 after infusion along with a blood sample for PK. If the biopsy (and associated PK sample) was not able to be performed on the Cycle 1 Day 15 visit, it should have been collected within the 24 hours after the tarloxotinib infusion or after another infusion day.

## 6.3.5 Biomarker Analysis

Blood samples were collected for biomarker assessment (e.g., circulating tumor deoxyribonucleic acid [ctDNA]) at the Cycle 1 Day 1, Cycle 2 Day 2, and End of Treatment visits. Biomarker assessment may include ctDNA mutation analysis and evaluation of the concordance of EGFR and HER2 mutation identification between blood and tumor tissue.

Version 1.0, 14 October 2022

Rain Therapeutics Inc. RAIN-701 SAP Study RAIN-701 Protocol Schedule Events (Protocol [Amendment 3] 24 October 2020) Table 2

1		SCR Cycle 1 (Day)		Cycle 1 (Day)	(Day)		Cycle 2 (Day) Cycles 3+ (Day)	Cycle 2 (Day)	(Day)		Ċ	cles 3	Cycles 3+ (Day)	(A)	OBX	$EOT^1$	FUP
X	Schedule of Events		1	∞	15	22		∞	15		1	∞	15	22			
X	Informed Consent	×															
X	Eligibility	X															
X	Medical/Disease History/	X															
$\begin{array}{cccccccccccccccccccccccccccccccccccc$	Smoking History																
X         X	Demographics	X															
X         X	Physical Examination	X	X				×				×					×	×
X         X	ECOG	X	×														
### The control of th	Weight	X	X				×				×					×	×
ead)³         X Vital Signs	X		×	×	Vital Signs	X														×	×
EOI         X	Pre-infusion		×	×	×	×	×	×	×	×	×	×	×	×			
ead)³         X EOI		×				EOI		×	×	×	×	×	×	×	×	×	×	×	×			
ead)  X         X </th <math>30</math>, <math>60</math>, and <math>90</math> min after <math>EOI^2</math>		×				$30$ , $60$ , and $90$ min after $EOI^2$		×	×	×	×	×	×	×	×	×	×	×	×			
tylusion         X	Electrocardiogram (12-lead) 	X														×	×
FOI = X	Pre-infusion		×	×	×	×	×	×	×	×	×	×	×	×			
Preol²         X EOI		×	×	×	×	×		EOI		×	×	×	×	×										
$\begin{array}{cccccccccccccccccccccccccccccccccccc$	I h after EOF		×	×	×	×	×										
rededed²         X<	2 h after EOF		×	×	×	×	×	×	×	×	×	×	×	×			
$\begin{array}{c ccccccccccccccccccccccccccccccccccc$	3 h after EOF		×	×	×	×	×										
reeded 	4 h after EOF		×	×	×	×	×	×	×	×	×	×	×	×			
X	hourly thereafter as needed $^2$		×	×	×	×	×	×	×	×	×	×	×	×			
X X X X X X X X X X X X X X X X X X X	Hematology Panel	X	X				×				×					×	×
	Serum Chemistry Panel	X	X	×	×	×	×	×	×	×	X	×	×	×		×	×

<sup>1 Day 1 of Cycles 2+ and EOT Visit are Day 28 of the prior cycle
 For subjects with Grade 3 QTcF prolongation (≥ 501 msec or 60 msec increase compared to pre-infusion), repeat ECG every 15 to 30 minutes until resolved to Grade 2 (481 to 500 msec) or lower (≤ 499 msec) and then obtain ECGs every hour. If QTcF prolongation is ≥ Grade 3, an ECG may need to be repeated more frequently during a subject's visit as indicated in Table 6 , depending on the degree of the prolongation and per institutional standards.  $^3$  For subjects with  $\geq$  Grade 3 ( $\geq$  500 msec) QTcF prolongation with current or prior infusion

-7	SCR		Cycle 1 (Day)	(Day)	_		Cycle 2 (Day)	(Day)		Cy	cles 3-	Cycles 3+ (Day)	()	OBX	$EOT^1$	FUP
Schedule of Events		1	∞	15	22	1	∞	15	22	1	∞	15	22			
Serum Potassium																
EOI		×				×										
$3 h after EOI^2$		×				×										
Urinalysis	×	×	×	×	×	×				×						×
Pregnancy Test 	×	×				×				×					×	
PK Samples																
Pre-infusion 		×				×										
$EOf^6$		×				×										
3 h after EOI 		×				×										
7 h after EOI 		X 7														
at optional tumor biopsy														X 5		
Biomarker Sample		X				X								Χş	X	
Potassium Supplementation 		×	×	×	×	×	×	×	×	×	×	×	×			
Tarloxotinib Infusion		×	×	×	×	×	×	×	×	×	×	×	×			
Tumor Tissue	×															
Optional Tumor Biopsy				X5										X	$X^9$	
Tumor Assessment	×			$\leftarrow$ Every 8 weeks (± 5 days) from Cycle 1 Day 1 $\rightarrow$	ry 8 w	eeks (±	5 day	s) fron	Cycle	1 Day	y 1 →					
Concomitant Medications	×					1	← Every Visit →	Visit –	^					×	×	
Adverse Events Assessment						1	$\leftarrow$ Every Visit $\rightarrow$	Visit –	 					×	×	×

Abbreviations: CT = computed tomography; ECOG = Eastern Cooperative Oncology Group; EOI = end of infusion; EOT = End-of-Treatment Visit; FUP = Follow-up Visit; MRI = magnetic resonance imaging; OBX = optional biopsy; PET = positron emissions tomography; PK = pharmacokinetic; QTcF = corrected QT interval as calculated according to Fridericia's formula; SCR = Screening Period

 $^4$  Serum pregnancy at baseline, then urine dipstick, for women of childbearing potential.  $^5$  Collect blood (plasma samples for PK and biomarker including ctDNA) at time of biopsy  $^6$  Can be made  $\pm 5$  minutes of scheduled event.

<sup>7 In a subset of subjects.

<sup>8 If applicable, see Section 6.2.2.
 Collect blood (plasma sample for biomarker) at time of biopsy

#### 7 SAMPLE SIZE AND POWER

The primary objective of this study is to determine if tarloxotinib provides a clinically significant tumor response to subjects in each cohort, investigated by assessing if the true ORR is at least above some desirable target level following therapy with tarloxotinib.

According to the protocol, a Simon's 2-stage minimax design (Simon 1989) was used for all cohorts. The null hypothesis that the true response rate is 15% was tested against a one-sided alternative. In the first stage, 21 subjects were accrued. If there were 3 or fewer responses among these 21 subjects, the cohort was stopped for futility. Otherwise, 22 additional subjects may be accrued for a total of 43 subjects in each cohort. The null hypothesis will be rejected if 11 or more responses are observed in 43 subjects. This design yields a type I error rate of 0.0454 and power of 0.8014 when the true response rate is 31%. The probability of early termination at the end of the first stage is 0.61 if the true response rate is 15%.

#### 8 ANALYSIS SETS

## 8.1 Intent-To-Treat Analysis Set

The Intent-To-Treat (ITT) Analysis Set will include all enrolled subjects regardless of Treatment Period eligibility or completion. The ITT Analysis Set will be the basis for demographics and baseline characteristics. Since enrolled subjects are subjects who received at least one dose of tarloxotinib, the ITT Analysis Set is functionally the same as the Primary Analysis Set.

## 8.2 Primary Analysis Set

The Primary Analysis Set (PAS), referred to as the Safety Population in the protocol, is defined as all subjects who subjects who received at least 1 dose of tarloxotinib. The Primary Analysis Set will be the analysis population for the safety and efficacy analyses.

#### 9.2 Definitions and Derived Variables

## 9.2.1 Screened and Enrolled Subjects

#### 9.2.1.1 Screened Subjects

Subjects who signed an informed consent form are considered Screened Subjects

## 9.2.1.2 Enrolled Subjects

Subjects who received at least one dose of tarloxotinib, are considered Enrolled Subjects.

## 9.2.2 Study Day

Study Day, which follows the CDISC Study Data Tabulation Model standard, is defined as (Assessment date - date of first study drug dosing + 1 day), where the assessment date is on or

after the date of first study drug dosing; (Assessment date - date of first study drug dosing), where the assessment date is before the date of first study drug dosing.

## 9.2.3 End of Study Treatment Definition

A subject is considered to have completed study treatment if the subject has completed the End of Treatment Visit.

## 9.2.4 End of Study Definition

A subject is considered to have completed the study if the subject has completed final safety follow-up visit. The end of the study is defined as the date of the last follow up visit of the last subject in the study.

#### 9.2.5 Date Last Known Alive

If a subject died, the date last known alive is the subject's date of death. Otherwise, the date last known alive is the date of last contact with the subject in the study (e.g., the most recent date of any in-clinic visit, date of telephone contact, date of withdrawal of consent, date of study completion date, etc.).

#### 9.2.6 Age

Age (years) will be calculated as the number of years between date of birth and date of the earliest informed consent, rounded down to the largest to a whole number less than or equal to the age at measurement.

#### 9.2.7 Body Mass Index

Body mass index  $(kg/m^2)$  is derived as weight (kg) / [height (m) × height (m)].

#### 9.2.8 Baseline Values

Baseline values are defined as the last, non-missing assessment prior to the first dose of study drug.

#### 9.2.9 Sum of Target Lesions

The sum of target lesions is defined as the sum of the longest diameters for non-nodal lesions and the short axis for lymph nodes.

## 9.2.10 Evaluable Subjects

A subject is classified as response evaluable if they have at least one response assessment or if they discontinue from treatment due to death prior to obtaining at least one response assessment. Subjects discontinuing treatment for disease progression must have a disease assessment performed documenting the progression

## **9.2.10.1 Responder**

All enrolled subjects who receive study treatment, have a baseline tumor assessment with documentation of measurable disease, have at least 1 on-study tumor assessment, whether or not this occurs at the specified imaging interval, will be considered evaluable for response. Subjects will be considered responders if they have a confirmed objective response of CR or PR according to RECIST v1.1 recorded from baseline until disease progression or death due to any cause.

## 9.2.11 RECIST Response Assessment

 Table 3
 Response Evaluation Criteria in Solid Tumours Guidelines

Response assessment	RECIST guideline, version 1.1				
Target lesions					
Complete Response	Disappearance of all target lesions and reduction in the short axis measurement of all pathologic lymph nodes to $\leq$ 10 mm				
Partial Response	≥30% decrease in the sum of the longest diameter of the target lesions compared with baseline				
Progressive Disease	≥20% increase of at least 5 mm in the sum of the longest diameter of the target lesions compared with the smallest sum of the longest diameter recorded OR The appearance of new lesions, including those detected by fludeoxyglucose PET				
Stable Disease	Neither partial response nor progressive disease				
Non-target lesions					
Complete Response	Disappearance of all non-target lesions and normalization of tumor marker levels				
Incomplete Response; Stable Disease	Persistence of 1 or more non-target lesions and/or the maintenance of tumor marker levels above normal limits				
Progressive Disease	The appearance of 1 or more new lesions or unequivocal progression				
If subject has measurable disease, an increase in the overall level or su worsening in non-target lesions, such that tumor burden has increased there is stable disease or partial response in target lesions					

If no measurable disease, an increase in the overall tumor burden comparable in magnitude with the increase that would be required to declare progressive disease in measurable disease (eg, an increase in pleural effusions from trace to large, or an increase in lymphangitic disease from localized to widespread)

#### 9.2.11.1 Overall Response Rate

The overall response rate in each cohort will be estimated as the number of subjects with a confirmed objective response (CR or PR) divided by the number of enrolled subjects (defined in Section 9.2.10) in each respective cohort.

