#### 4 PURPOSE OF THE ANALYSIS PLAN

This statistical analysis plan (SAP) pre-specifies the statistical analysis methods for supporting the completion of the abbreviated clinical study report (CSR) of Study RAIN-701 for investigational product tarloxotinib, a novel drug candidate designed to treat subjects with advanced solid tumors with qualifying genetic mutations and/or fusions. The study intended to enroll up to 215 subjects across 5 cohorts but was discontinued early on the basis of a business decision made by the sponsor. At the time of the database lock for RAIN-701 (23 April 2021), 41 subjects were enrolled. This SAP will be used to conduct a comprehensive safety analysis and summarize the available efficacy data collected during the study. The primary, secondary, and efficacy analyses planned in the protocol may not be appropriate or possible based on the available data. The planned analyses identified in this SAP may be included in future manuscripts.

The analysis methods described in this plan are considered *a posterior*, in that they have been defined after the clinical database lock. Exploratory analyses that are not defined in this SAP may be performed to support the clinical development program. Any post-hoc or unplanned analyses that are performed for the CSR, but not defined in this SAP, will be documented in the CSR. Changes from the planned analyses stated in the study protocol are described in Section 15. Should the SAP and the protocol be inconsistent with respect to any further planned analyses, the language of the SAP is governing.

Version 1.0, 14 October 2022

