#### 15 CHANGES RELATIVE TO THE PROTOCOL-SPECIFIED ANALYSIS

Protocol Section 9.2.3 states "Deviations will be defined prior to database lock. Handling of major deviations in statistical analyses will be defined in the SAP" and further defines a Per-Protocol analysis set excludes subjects with certain, pre-specified deviations. RAIN-701 was terminated and the analysis will support an abbreviated clinical study report, which does not include protocol deviations per FDA guidance for industry, Submission of Abbreviated Reports and Synopses in Support of Marketing Applications. Analysis will be performed on the safety population which includes all subjects who received at least 1 dose of tarloxotinib. Analysis of a Per Protocol (PP) population where subjects with major protocol deviations are removed is not necessary for the aCSR. The abbreviated CSR will provide a comprehensive safety analysis for all subjects receiving at least 1 dose of tarloxotinib. Additionally, the primary efficacy analysis of ORR will include all treated subjects. Efficacy analyses are not interpretable as RAIN-701 was terminated and did not enroll the intended sample size to support statistical analyses.

Protocol Section 7 states, "In accordance with RECIST v1.1, response (PR and CR) must be confirmed by a second tumor assessment at least 8 weeks after the initial observed response." SAP Section 6.3.1 text instead states that the confirmation assessment must be at least 4 weeks after the initial observed response, which is aligned with the true RECIST v1.1 criteria. The efficacy endpoint (Section 9.2.13) still follows the protocol text in defining the disease control for at least 8 weeks (2 cycles).

Protocol Table 12 states "Microscopic sediment evaluation, as clinically indicated" as a urinalysis assessment, but these microscopic sediment urinalysis assessments were not collected. Similarly, Protocol Table 12 lists ALP as a serum chemistry assessment, but it was not collected.

Units and reference ranges of the local laboratory assessments were not collected. The Sponsor has assigned units and lab normal ranges for each parameter (e.g., lower limit of normal, upper limit of normal) based on available information and Harrison's Principles of Internal Medicine (Appendix A).

Rain Therapeutics Inc. RAIN-701 SAP

Version 1.0, 14 October 2022

Adverse events were coded with MedDRA version 22.0 and medical history events were coded with MedDRA version 23.0.

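### The SAP's formula for the primary response rate names enrolled subjects but points to the definition of response-evaluable subjects (minor; correct the reference)

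*SAP*

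**What the plan says.** SAP 9.2.11.1 gives the response rate for each cohort as confirmed CR or PR "divided by the number of enrolled subjects (defined in Section 9.2.10) in each respective cohort". The best overall response rate in 9.2.11.2 is calculated in the same way.

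The section cited, SAP 9.2.10, is about evaluability. Its lead paragraph begins "A subject is classified as response evaluable if they have at least one response assessment", and it also keeps subjects whose treatment ended in death before any assessment. It adds: "Subjects discontinuing treatment for disease progression must have a disease assessment performed documenting the progression". Its subsection 9.2.10.1 gives another rule: study treatment, measurable disease documented at baseline, and at least one on-study tumor assessment.

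Enrolment is defined in SAP 9.2.1.2: "Subjects who received at least one dose of tarloxotinib, are considered Enrolled Subjects". On the analysis population, SAP 8.1 says that "the ITT Analysis Set is functionally the same as the Primary Analysis Set", SAP 8.2 says "The Primary Analysis Set will be the analysis population for the safety and efficacy analyses", and SAP 15 says that "the primary efficacy analysis of ORR will include all treated subjects". SAP 9.2.13 divides disease control by the number enrolled and has no cross-reference.

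The protocol points both ways. Section 9.2.3 names all treated patients as the primary efficacy population, while 9.6.1.2 divides by evaluable patients. Where the two documents differ, SAP 4 states that "the language of the SAP is governing".

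**The concern.** The noun in the formula and the definition attached to it describe different sets of subjects. A wrong reference often leads nowhere and is noticed. This one leads to a usable denominator that resembles the protocol's own formula, so someone who follows it would have little reason to suspect an error. The output would then conflict with SAP 8.2 and SAP 15.

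The subjects at issue are treated subjects with no post-baseline assessment. They cannot be confirmed responders, so removing them from the denominator works in one direction only. A subject stopped for clinical progression without a scan shows the conflict: not evaluable under SAP 9.2.10, but a non-responder under protocol 9.2.3.

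ORR by cohort with an exact 95% interval is the leading efficacy summary of the abbreviated report (SAP 13.2), and SAP 4 allows the planned analyses to go into manuscripts. The cohorts are small enough for one subject to be visible in the rate.

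**Working it through.** **1. The plan's own figures.** SAP 7 and protocol 9.1 state a type I error of 0.0454, power of 0.8014 and early termination probability of 0.61 for the two-stage design (stop at 3 or fewer of 21; reject at 11 or more of 43). The rejection probability is the sum over first-stage counts x = 4 to 21 of P(X1 = x) × P(X2 ≥ 11 − x), with X1 binomial on 21 and X2 binomial on 22. This gives 0.0454 at a true rate of 15% and 0.8014 at 31%; P(X1 ≤ 3) at 15% is 0.611. All three reproduce, and none depends on the cross-reference.

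**2. Candidate denominators in the SAP text.**

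| Reading | Source | Treated, died before any assessment | Treated, stopped for clinical progression without a scan |
|---|---|---|---|
| Enrolled | 9.2.1.2 | counted | counted |
| Evaluable, lead paragraph | 9.2.10 | counted, if death was the reason for discontinuing | dropped |
| Evaluable, subsection | 9.2.10.1 | dropped | dropped |

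Following the reference therefore does not even settle on a single denominator.

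**3. Direction.** Let n be the number enrolled in a cohort, x the confirmed responders, and k the treated subjects dropped for having no post-baseline assessment. None of the k is a responder, so x/n becomes x/(n − k), a multiplication by n/(n − k). This is 1 when k = 0 and above 1 otherwise. If x = 0 the rate stays at zero.

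**4. Size for k = 1**, with n from SAP Table 1:
- Cohort A: 11/10 = 1.10
- Cohort B: 22/21 = 1.05
- Cohort C: 8/7 = 1.14

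**5. Illustration.** The documents give neither x nor k. Assume x = 2 in each cohort; intervals are exact (Clopper-Pearson) 95%.

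| Cohort | k = 0 | k = 1 | k = 2 |
|---|---|---|---|
| A | 2/11 = 18.2% (2.3 to 51.8) | 2/10 = 20.0% (2.5 to 55.6) | 2/9 = 22.2% (2.8 to 60.0) |
| B | 2/22 = 9.1% (1.1 to 29.2) | 2/21 = 9.5% (1.2 to 30.4) | 2/20 = 10.0% (1.2 to 31.7) |
| C | 2/8 = 25.0% (3.2 to 65.1) | 2/7 = 28.6% (3.7 to 71.0) | 2/6 = 33.3% (4.3 to 77.7) |

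For k = 1 the shifts are 1.8, 0.4 and 3.6 percentage points. The k = 0 intervals are 49.5, 28.1 and 61.9 points wide (51.8 − 2.3, 29.2 − 1.1, 65.1 − 3.2). Other values of x and k give other shifts, so these are examples and not bounds.

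**The case against.** The best reply is that the SAP already answers the question. The word in the formula is a defined term, Table 1 has a column of enrolled numbers (11, 22 and 8, total 41), SAP 8.2 and 15 place the efficacy analysis on all treated subjects, and the disease control formula uses the enrolled number without qualification. Two other references in the SAP are wrong in the same way: 12.1 cites 9.2.11 for dose intensity, which is defined in 9.2.16, and 12.2 cites 9.2.10 for medications, which are defined in 9.2.17. That pattern suggests sections were renumbered, not that a denominator was chosen. Most of this stands, and it is why the point is minor.

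It does not remove the error. To reach the intended reading, a programmer must set aside the definition that the formula itself cites. SAP 15 announces that ORR covers all treated subjects but does not say that the denominator in protocol 9.6.1.2 has been replaced.

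A reader might infer more than the documents support:
- That the SAP deliberately moved the primary endpoint to evaluable subjects. SAP 8.2 and 15 say the opposite.
- That the reported ORR is inflated. Nothing shows that the reference was followed, or that any treated subject lacked an assessment.
- That the go/no-go rule or error rates are compromised. SAP 9.1 rules out efficacy tests, and SAP 15 itself regards the efficacy analyses as not interpretable after early termination.
- That an evaluable denominator would plainly breach the protocol. The protocol is mixed: 9.6.1.2 uses one, and 9.2.3 also treats patients removed before assessment for reasons other than clinical progression as unevaluable.

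**Conclusion.** The formula is wrong as written, and the severity is minor. The intended denominator can be recovered from the rest of the SAP: all treated subjects in each cohort.

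If the reference were followed, ORR would be unchanged or higher, by a factor of 1.10 (A), 1.05 (B) or 1.14 (C) for one dropped subject in a cohort with at least one responder. That result rests only on the enrolled numbers in Table 1 and on the fact that a subject with no post-baseline assessment cannot have a confirmed response. The percentages and intervals in the illustration also rest on assumed counts. With no such subjects, the readings agree. The reach is limited to the descriptive ORR, its exact interval and the best-response summary.

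**What to change.** In SAP 9.2.11.1, change the cross-reference from Section 9.2.10 to Section 9.2.1.2. The denominators are then 11, 22 and 8, and treated subjects without a post-baseline assessment count as non-responders. The best overall response rate follows automatically through 9.2.11.2.

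In SAP 15, add one sentence saying that the all-treated denominator replaces the evaluable denominator of protocol 9.6.1.2.

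The cost is one corrected reference and one sentence; neither the protocol nor the data collection changes. The only downside is that the reported ORR may be slightly lower than it would be on an evaluable denominator. The stale references in SAP 12.1 and 12.2 could be corrected in the same revision.
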